12.2.2.2 Safety Analysis Set for Vaccination at 2 Months of Age (SafAS1)

The SafAS1 for vaccination at 2 months of age is defined as those subjects who have received at least one dose of the study vaccines at Visit 1 around 2 months of age and have any safety data available. All subjects will have their safety analyzed after Visit 1 dose according to the vaccines they actually received at Visit 1.

The subjects received at least one dose of study vaccines but out of the planned vaccination schedule at Visit 1 will be classified to “Other” group. The safety analysis tables will not present data for ‘Other’ group at Visit 1, and the safety data for ‘Other’ group at Visit 1 will be listed only.

Safety data recorded for a vaccine received out of the protocol design at Visit 1 will be excluded from the analysis (and listed separately).

12.2.2.3 Safety Analysis Set for Vaccination at 3 Months of Age (SafAS2)

The SafAS2 for vaccination at 3 months of age is defined as those subjects who have received at least one dose of the study vaccines at Visit 2 around 3 months of age and have any safety data

available. All subjects will have their safety analyzed after Visit 2 dose according to the vaccines they actually received at Visit 2.

The subjects received at least one dose of study vaccines but out of the planned vaccination schedule at Visit 2 will be classified to “Other” group. The safety analysis tables will not present data for ‘Other’ group at Visit 2, and the safety data for ‘Other’ group at Visit 2 will be listed only.

Safety data recorded for a vaccine received out of the protocol design at Visit 2 will be excluded from the analysis (and listed separately).

12.2.2.4 Safety Analysis Set for Vaccination at 4 Months of Age (SafAS3)

The SafAS3 for vaccination at 4 months of age is defined as those subjects who have received at least one dose of the study vaccines at Visit 3 around 4 months of age and have any safety data available. All subjects will have their safety analyzed after Visit 3 dose according to the vaccines they actually received at Visit 2 and Visit 3. For subjects who received Bexsero[®] vaccine and at least one dose of routine vaccines at Visit 3, who received MenACYW conjugate vaccine and at least one dose of routine vaccines at Visit 2 will be analyzed under “Group 1 + Group 2” combined group, while subjects who received Bexsero[®] and at least one dose of routine vaccines at Visit 3 but only received at least one dose of routine vaccines without MenACYW conjugate vaccine at Visit 2 will be analyzed under “Group 3”.

The subjects received at least one dose of study vaccines but out of the planned vaccination schedule at Visit 3 will be classified to “Other” group. The safety analysis tables will not present data for ‘Other’ group at Visit 3, and the safety data for ‘Other’ group at Visit 3 will be listed only.

Safety data recorded for a vaccine received out of the protocol design at Visit 3 will be excluded from the analysis (and listed separately).

12.2.2.5 Safety Analysis Set for Vaccination at 12-13 Months of Age (SafAS4)

The SafAS4 for vaccination at months of age is defined as those subjects who have received at least one dose of the study vaccines at Visit 4 around 12 to 13 months of age and have any safety data available. All subjects will have their safety analyzed after Visit 4 dose according to the vaccine(s) they actually received at Visit 4.

The subjects received at least one dose of study vaccines but out of the planned vaccination schedule at Visit 4 will be classified to “Other” group. The safety analysis tables will not present data for ‘Other’ group at Visit 4, and the safety data for ‘Other’ group at Visit 4 will be listed only.

Safety data recorded for a vaccine received out of the protocol design at Visit 4 will be excluded from the analysis (and listed separately).

12.2.3 Per-Protocol Analysis Set

The per-protocol analysis set (PPAS) is a subset of the FAS. Immunogenicity analyses will primarily be performed on PPAS. There will be three Per-Protocol Sets (PPASs) for this study according to the three FASs:

- PPAS for immunogenicity evaluation after infant vaccination (4 months of age, PPAS1)
- PPAS for immunogenicity persistence evaluation after infant vaccination (12 to 13 months of age, PPAS2)
- PPAS for second year of life vaccination (PPAS3)

12.2.3.1 Per-Protocol Set for immunogenicity evaluation after infant vaccination (4 months of Age, PPAS1):

The PPAS1 is a subset of the FAS1.

Post-vaccination serology obtained at Visit 3 (4 months of age) for all meningococcal antigens (A, C, W and Y) will be used for immunogenicity analyses of infant stage of the study.

The subjects presenting with at least one of the following relevant protocol deviations will be excluded from the PPAS1:

- Subject did not meet all protocol-specified inclusion criteria or met at least one of the protocol-specified exclusion criteria
- Subject did not complete the vaccination schedule for infant stage from Visit 1 to Visit 3
- Subject received a vaccine other than the one that he / she was randomized to receive for infant stage from Visit 1 to Visit 3
- Preparation and / or administration of vaccine was not done as per-protocol for infant stage from Visit 1 to Visit 3
- Subject did not receive vaccine in the proper time window for infant stage from Visit 1 to Visit 3:
 - Visit 1: ≥ 56 to ≤ 89 days of age
 - Visit 2: Visit 1 + 30 days (+14 days)
 - Visit 3: Visit 2 + 30 days (+14 days)
- Subject did not provide a post-dose serology sample in the proper time window or a post-dose serology sample was not drawn at Visit 3:
 - Blood sampling Visit 3: Visit 2 + 30 days (+14 days)
- Subject received a protocol-prohibited therapy / medication / vaccine (reportable concomitant medication of category 2 and / or category 3)
- Subject had other protocol violations that affected the subject's immune response, as determined by the clinical team before locking the database.

In addition to the reasons listed above, subjects will also be excluded from the PPAS1 if their serology sample did not produce a valid test result at Visit 3.

Vaccine correctness required by the PPAS1 includes not only the 1 dose of MenACYW conjugate vaccine for Group 1 and Group 2, and the 2 doses of Bexsero[®] for Groups 1 to 3, but also the concomitant routine vaccines as scheduled (Infanrix hexa[®], Rotarix[®], and Prevenar 13[®]) for Groups 1 to 3 during infant stage from Visit 1 to Visit 3.

In the event of a local or national immunization program with a pandemic influenza or coronavirus vaccine, subjects who receive 1 or more doses of a pandemic influenza or coronavirus vaccine, or the vaccine listed above at any time during the study will not be withdrawn from the study.

12.2.3.2 Per-Protocol Set for immunogenicity persistence evaluation after infant vaccination (12 to 13 Months of Age, PPAS2)

The PPAS2 is a subset of the FAS2.

Post-vaccination (after infant vaccination) serology obtained at Visit 4 (12 to 13 months of age) prior to toddler vaccination for all meningococcal antigens (A, C, W and Y) will be used for immunogenicity persistence analyses of infant stage of the study.

The subjects presenting with at least one of the following relevant protocol deviations will be excluded from the PPAS2:

- Subject did not meet all protocol-specified inclusion criteria or met at least one of the protocol-specified exclusion criteria
- Subject did not complete the vaccination schedule for infant stage from Visit 1 to Visit 3
- Subject received a vaccine other than the one that he / she was randomized to receive for infant stage from Visit 1 to Visit 3
- Preparation and / or administration of vaccine was not done as per-protocol for infant stage from Visit 1 to Visit 3
- Subject did not receive vaccine in the proper time window for infant stage from Visit 1 to Visit 3:
 - Visit 1: ≥ 56 to ≤ 89 days of age
 - Visit 2: Visit 1 + 30 days (+14 days)
 - Visit 3: Visit 2 + 30 days (+14 days)
- Subject did not provide a post-dose (after infant vaccination) serology sample in the proper time window or a post-dose serology sample was not drawn at Visit 4:
 - Blood sampling Visit 4: 12 to 13 months of age prior to toddler vaccination
- Subject received a protocol-prohibited therapy / medication / vaccine (reportable concomitant medication of category 2 and / or category 3)

- Subject had other protocol violations that affected the subject's immune response, as determined by the clinical team before locking the database.

In addition to the reasons listed above, subjects will also be excluded from the PPAS2 if their serology sample did not produce a valid test result at Visit 4.

Vaccine correctness required by the PPAS2 includes not only the 1 dose of MenACYW conjugate vaccine for Group 1 and Group 2, and the 2 doses of Bexsero[®] for Groups 1 to 3, but also the concomitant routine vaccines as scheduled (Infanrix hexa[®], Rotarix[®], and Prevenar 13[®]) for Groups 1 to 3 during infant stage from Visit 1 to Visit 3.

In the event of a local or national immunization program with a pandemic influenza or coronavirus vaccine, subjects who receive 1 or more doses of a pandemic influenza or coronavirus vaccine, or the vaccine listed above at any time during the study will not be withdrawn from the study.

12.2.3.3 Per-Protocol Set for Second Year of Life Vaccination (12 to 13 Months of Age, PPAS3):

The PPAS3 is a subset of the FAS3.

During the second year of life, the immunogenicity analyses for meningococcal antigens (A, C, W and Y) are performed on serology obtained at Visit 5, which is 30 days after the administration of study vaccine(s) at Visit 4.

The subjects presenting with at least one of the following relevant protocol deviations will be excluded from the PPAS2:

- Subject did not meet all protocol-specified inclusion criteria or met at least one of the protocol-specified exclusion criteria
- Subject did not complete the vaccination schedule, including the infant schedule and the 12 to 13 months vaccination in second year of life, from Visit 1 to Visit 4
- Subject received a vaccine other than the one that he / she was randomized to receive during the infant stage or second year of life, from Visit 1 to Visit 4
- Preparation and / or administration of vaccine was not done as per-protocol during the infant stage or second year of life, from Visit 1 to Visit 4
- Subject did not receive vaccine in the proper time window during the second year of life:
 - Visit 4: 12 to 13 months of age
- Subject did not provide a post-dose serology sample in the proper time window or a post-dose serology sample was not drawn at Visit 5 in the second year of life:
 - Blood sampling 3 (Visit 5): Visit 4 + 30 days (+21 days)
- Subject received a protocol-prohibited therapy / medication / vaccine during the infant stage or second year of life prior to or at Visit 5

- Subject had other protocol violations during the infant stage or second year of life from Visit 1 to Visit 5, which affected the subject's immune response, as determined by the clinical team before locking the database

In addition to the reasons listed above, subjects will also be excluded from the PPAS3 if their serology sample did not produce a valid test result at Visit 5 in the second year of life.

Vaccine correctness required by the PPAS3 includes the dose of MenACYW conjugate vaccine for Group 1, the dose of MenACYW conjugate vaccine and the dose of Bexsero[®] for Group 2, and the dose of Bexsero[®] for Group 3 in the second year of life at Visit 4.

In the event of a local or national immunization program with a pandemic influenza or coronavirus vaccine, subjects who receive 1 or more doses of a pandemic influenza or coronavirus vaccine, or the vaccine listed above at any time during the study will not be withdrawn from the study.

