* This call is made 8 days after the respective vaccinations. If day 8 falls on a weekend or holiday, the telephone call may be made on the following business day. During this telephone call, the staff will find out whether the subject experienced any SAE not yet reported and will remind the subject's parent / legally acceptable representative to continue using the diary card, and confirm the date and time of the next visit.

† Visit 4 may occur anytime from the day the subject becomes 12 months of age until the day before becoming 14 months of age.

‡ Routine pediatric vaccines may be given as per standard of care outside of the study, after all visit procedures have been completed.

§ Physical examination should be performed as per standard of care.

** A health assessment will be performed by a study nurse at Visit 4. A physical examination may be performed on the basis of relevant medical history/study nurse health assessment according to the investigator's clinical judgment.

†† Temperature (route as per standard of care) needs to be measured before each vaccination and recorded in the source documents.

‡‡ Should a subject receive oral or injectable antibiotic therapy within 3 days prior to any blood draw, the investigator will postpone that blood draw until it has been 3 days since the subject last received oral or injectable antibiotic therapy. Postponement must still be within the timeframe for blood draw. If postponement would result in the sample collection falling outside of this timeframe, the blood sample should be collected without postponement, and it should be documented appropriately that the sample was taken less than 3 days after stopping antibiotic treatment.

§§ Blood sample will be drawn prior to vaccination.

*** Blood samples will be drawn from ~ 70 randomized subjects only (Subset A).

††† Blood samples will be drawn from ~ 90 randomized subjects only (Subset B).

‡‡‡ A physical examination may be performed on the basis of relevant medical history at the time of the visit according to the investigator's clinical judgment.

§§§ Routine pediatric vaccines: At Visit 1: Infanrix hexa[®], Rotarix[®], Prevenar 13[®]; at Visit 2: Infanrix hexa[®], Rotarix[®]; at Visit 3: Infanrix hexa[®], Prevenar 13[®]

**** The diary card dispensed to the subject's parent/legally acceptable representative at each visit must correspond to the number of injections given at that visit.

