Note: Each visit may be conducted at the site (site visit) or at the subject's home (home visit).

Blood Sampling

Subjects will provide the following blood samples:

- Groups 1 and 2: 160 subjects in each group will be randomized to have 3 blood draws at the intervals mentioned below. The remaining subjects will only have 1 blood draw at Visit 5.
- Group 3: all 160 subjects will have 3 blood draws.

For the subjects randomized to have 3 blood draws in Group 1 and Group 2, the first 2 blood draws will be performed in a staggered way – approximately half of the subjects (~70 subjects in each group) will have blood draws at Visit 2 and Visit 3 (subset A), and the remaining half (~90 subjects in each group) will have blood draws at Visit 3 and Visit 4 (subset B). The third blood draw will be performed at Visit 5 for all subjects.

Subset A (~70 subjects in each group):

- a pre-vaccination blood sample at Visit 2
- a blood sample at Visit 3 (30 days after vaccination at Visit 2)
- a blood sample at Visit 5 (30 days after vaccination at Visit 4)

Subset B (~90 subjects in each group):

- a blood sample at Visit 3 (30 days after vaccination at Visit 2)
- a pre-vaccination blood sample at Visit 4
- a blood sample at Visit 5 (30 days after vaccination at Visit 4)

For the subjects randomized to Group 3, the first 2 blood draws will be performed in a staggered way – approximately half of the subjects (~70 subjects) will have blood draws at Visit 2 and Visit 3 (subset A), and the remaining half (~90 subjects) will have blood draws at Visit 3 and Visit 4 (subset B). The third blood draw will be performed at Visit 5 for all subjects.

Subset A (~70 subjects):

- a pre-vaccination blood sample at Visit 2
- a blood sample at Visit 3 (30 days after vaccination at Visit 2)
- a blood sample at Visit 5 (30 days after vaccination at Visit 4)

Subset B (~90 subjects):

- a blood sample at Visit 3 (30 days after vaccination at Visit 2)
- a pre-vaccination blood sample at Visit 4
- a blood sample at Visit 5 (30 days after vaccination at Visit 4)

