 - Rotarix[®]: administer orally per instructions in the package insert

It is recommended that MenACYW conjugate vaccine and Infanrix hexa[®] be administered in opposite limbs. If multiple vaccines are administered at a single visit, each vaccine should be administered at a different anatomic site. If vaccines are given in the same limb, the injection sites should be separated by 1 inch or more, so that any local reactions can be differentiated.
- 9) Observe the subject for 30 minutes and record any AEs in the source document. In the event of a local reaction, indicate the associated vaccine.
- 10) Give the parent / legally acceptable representative a diary card (the diary card should match the number of injections given during this visit, 2 injections for Groups 1 and 2, and 1 injection for Group 3).
- 11) Remind the parent / legally acceptable representative to expect a telephone call 8 days after Visit 2.
- 12) Remind the parent / legally acceptable representative to notify the site in case of an SAE.

13) Complete the relevant CRFs for this visit.

Telephone Call 2 (8 days after Visit 2)

Refer to steps in Telephone Call 1.

Visit 3 (30 [+14] days after Visit 2): Collection of Safety Information, Vaccination, and Blood Sample

- 1) Collect and review the diary card with the parent / legally acceptable representative, including any AEs, medications, or therapy that occurred since vaccination. If an SAE, including an AESI, has occurred, follow the instructions in [Section 10](#) for reporting it.
- 2) Measure temperature. If the temperature is $\geq 38^{\circ}\text{C}$, postpone vaccination until the condition is resolved.
- 3) Review temporary contraindications for blood sampling. Ensure the subject has not had any antibiotics within the previous 72 hours (3 days).
- 4) Collect 3 mL of blood from subjects in Subset A (BL2), and from subjects in Subset B (BL1) (see [Section 5.1.2](#) and [Section 5.1.3](#) for definition of Subset A and Subset B and details of the sample schedule, and [Section 7.1](#) for detailed instructions regarding the handling of blood samples).
- 5) Review warnings and precautions to vaccinations.
- 6) Review contraindications to subsequent vaccinations and conditions for withdrawal.
- 7) Contact the IRT system for vaccine assignment.
- 8) Administer the following study vaccines. Each vaccine should be administered in the assigned location and documented appropriately.

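### PPAS1 drops valid Visit 3 titers because of vaccine deviations that happen after the Visit 3 blood draw

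*Protocol*

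**What the plan says.** Protocol section 12.2.3.1 names the sample that PPAS1 serves: "Post-vaccination serology obtained at Visit 3 (4 months of age) for all meningococcal antigens". Section 5.1.1 says what that sample measures, for Subset A and Subset B alike: "a blood sample at Visit 3 (30 days after vaccination at Visit 2)".

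The order of events at Visit 3 is stated three times:
- Section 5.1.4, Visit 3, has the draw at step 4 ("Collect 3 mL of blood from subjects in Subset A (BL2), and from subjects in Subset B (BL1)") and the vaccines at step 8 ("Administer the following study vaccines").
- The schedule footnotes for all three groups say "Blood sample will be drawn prior to vaccination".
- The legend to Table 5.1 in section 5.1.3 says the same.

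The PPAS1 exclusions nevertheless extend to the Visit 3 vaccines. The first of them is "Subject did not complete the vaccination schedule for infant stage from Visit 1 to Visit 3". The criteria on receipt of the randomized vaccine, on preparation and administration, and on the vaccination window cover the same three visits. The vaccine-correctness statement that follows confirms this reading, because it requires the MenACYW dose "and the 2 doses of Bexsero[®] for Groups 1 to 3, but also the concomitant routine vaccines as scheduled". Section 6.1.2.3 places the second infant Bexsero dose at 4 months of age, which is Visit 3.

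**The concern.** A per-protocol set should remove subjects whose deviation could have altered the measurement being analysed. The Visit 3 titer is fixed once the blood is drawn, and a Visit 3 vaccine given afterwards, or not given, cannot alter it. As written, PPAS1 discards such titers.

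Section 12.2.4 makes the per-protocol sets the main sets for immunogenicity. What is at stake is a loss of usable samples from the description of the first-dose response (secondary objective 2) and from the Group 3 Visit 3 results. The paired Visit 2 and Visit 3 data come only from Subset A, about 70 subjects per group, so that is where a loss would be felt most.

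**Working it through.** The protocol gives no size or power for PPAS1, so there is no stated figure to reproduce. The stated power of 88.4% concerns the primary objective at Visit 5 and does not depend on this rule. The check has two parts.

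**1. Last vaccination counted against the sample analysed**

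| Set | Named sample | Last vaccination that counts | Given before the sample? |
|---|---|---|---|
| PPAS1 (12.2.3.1) | Visit 3, drawn before that visit's vaccines | Visit 3 | No |
| PPAS2 (12.2.3.2) | Visit 4, drawn before toddler vaccination | Visit 3 | Yes |
| PPAS3 (12.2.3.3) | Visit 5 | Visit 4 | Yes |

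PPAS1 is the only set whose vaccination criteria run past its own sample. Its four vaccination criteria match those of PPAS2, where they fit. The timing of the Visit 3 draw is already policed by a separate PPAS1 criterion ("Subject did not provide a post-dose serology sample in the proper time window"), so the vaccination criteria are not needed for that purpose.

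A route to such an exclusion exists. At Visit 3 a temperature of 38°C or above postpones vaccination (section 5.1.4), while the only temporary contraindication to a blood draw listed in section 5.2.7.1 is recent antibiotic use. As written, blood can be drawn in window while vaccination is deferred. If the deferred doses are then missed or late, the titer leaves PPAS1. A wrong or mis-administered Visit 3 vaccine has the same result.

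**2. Size**

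Inputs: 160 subjects per group with a planned Visit 3 draw, of whom about 70 are in Subset A (section 5.1.1). The share lost, *r*, is not in the protocol; 2%, 5% and 10% are assumptions. The number remaining is *n*(1 − *r*), as a whole number. The half-width is that of the Clopper-Pearson 95% interval with *x* about *n*/2 responders, where the lower limit is the 0.025 quantile of Beta(*x*, *n* − *x* + 1), the upper limit is the 0.975 quantile of Beta(*x* + 1, *n* − *x*), and the half-width is half the difference.

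| Start | Lost | Remaining | Half-width (points) | Change |
|---|---|---|---|---|
| 160 | 0% | 160 | 8.00 | – |
| 160 | 2% | 157 | 8.07 | 0.07 |
| 160 | 5% | 152 | 8.21 | 0.21 |
| 160 | 10% | 144 | 8.44 | 0.44 |
| 70 | 0% | 70 | 12.20 | – |
| 70 | 2% | 69 | 12.29 | 0.09 |
| 70 | 5% | 66 | 12.57 | 0.37 |
| 70 | 10% | 63 | 12.87 | 0.67 |

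Over every starting number from 70 to 160 at these three loss rates, rounding to the nearest whole subject, the largest change is 0.68 points (76 to 68). At a 90% response rate the half-width goes from 4.95 to 5.18 points for 160 to 144, and from 7.70 to 8.00 for 70 to 63.

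Both starting numbers are planned ceilings before any attrition. If the study-wide 30% non-adherence of section 12.5 applied to Subset A, 70 × 0.70 = 49 would remain. A further loss to 44 would move the half-width from 14.62 to 15.44 points, a change of 0.82.

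**The case against.** The strongest reply is that the rule looks deliberate. The vaccine-correctness statement spells out the doses required through Visit 3, and PPAS1 and PPAS2 share the same infant-stage criteria, which amounts to one definition of a per-protocol infant course. A per-protocol set may be stricter than a single sample needs, and separating the two sets would let Visit 3 titers be reported under two vaccination definitions, one for the dose response and one for persistence.

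This explains how the wording may have arisen, but the protocol does not give it as a reason. The two sets already differ in the sample they require, and Subset A has no Visit 4 draw, so it cannot enter PPAS2 at all. Persistence is assigned to PPAS2 by section 12.2.4 and would keep its present requirement.

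Other points on that side stand and limit the finding:
- The affected results are descriptive, with no hypothesis tested (sections 12.1.2.1 and 12.1.3).
- FAS1 keeps every affected titer (section 12.2.1.1), though only for exploratory analysis.
- Postponed vaccination must stay within the vaccination window (section 5.2.7.1), so the vaccination window largely overlaps the sample window.
- Subjects with a definitive contraindication known before Visit 3 go to safety-only follow-up (section 5.2.7.3) and may have no Visit 3 sample to lose.

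**Conclusion.** The concern holds. PPAS1 excludes valid, in-window post-dose-1 titers for events that come after the sample, and nothing in the protocol justifies it. The reading of the text is firm; the practical effect is small. It rests on an assumed loss of 2% to 10%, since the number of such deviations cannot be derived. Under that assumption the half-width at a 50% rate grows by at most about 0.7 points from the planned numbers, or about 0.8 points if Subset A had already shrunk to 49. The primary objective, assessed on PPAS3, is unaffected, and no bias between groups is claimed. This is a worthwhile correction of wording and does not threaten the trial's conclusions.

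**What to change.** In section 12.2.3.1, limit the completion, vaccine-identity, preparation/administration and vaccination-window criteria to Visits 1 and 2, and amend the PPAS1 vaccine-correctness statement to match. Keep the Visit 3 sample-window and valid-result criteria. Leave PPAS2 and PPAS3 vaccination criteria as they are, so that persistence is still analysed in subjects who received the Visit 3 doses.

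The change should be made before database lock. Visit procedures, sampling and vaccination are unaffected. Because the rule is in the protocol, it needs a written amendment and at least notification of the ethics committee under section 5.4. Section 12.1 says the analysis plan is written in accordance with the protocol, so it should carry the same definition.

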5.1 Description of the Overall Study Design and Plan

5.1.1 Study Design

This study is a Phase III, open-label, randomized, parallel-group, active-controlled, multi-center study to evaluate the immunogenicity and describe the safety of MenACYW conjugate vaccine when administered concomitantly with a meningococcal group B vaccine (Bexsero[®]) and other routine pediatric vaccines as part of the National Immunization Schedule in healthy infants and toddlers in the UK.

Approximately 800 healthy infants aged ≥ 56 to ≤ 89 days (approximately 2 months of age) will be randomized 2:2:1 to the following 3 groups:

Group 1: MenACYW conjugate vaccine at 3 months and at 12 to 13 months of age; Bexsero[®] at 2, 4, and 12 to 13 months of age

Group 2: MenACYW conjugate vaccine at 3 months and at 12 to 13 months of age; Bexsero[®] at 2 and 4 months of age

Group 3: Bexsero[®] at 2, 4, and 12 to 13 months of age

Routine pediatric vaccines will be given to subjects in all groups according to the UK immunization schedule:

- Infanrix hexa[®] (Combined Diphtheria-Tetanus-acellular Pertussis [DTPa], Hepatitis B, Inactivated Poliovirus and *Haemophilus influenzae* type b Vaccine; DTPa-HBV-IPV+Hib) at 2, 3, and 4 months of age
- Rotarix[®] (rotavirus vaccine; RV) at 2 and 3 months of age
- Prevenar 13[®] (pneumococcal 13-valent conjugate vaccine; PCV13) at 2 and 4 months of age

The routine vaccines (Infanrix hexa[®], Rotarix[®], and Prevenar 13[®]) will be sourced by the investigators and administered as per the standard practices. MenACYW conjugate vaccine and Bexsero[®] will be provided by the Sponsor.

The routine pediatric vaccines administered in the second year of life (Menitorix[®], Priorix[®]/M-M-RVAXPRO[®], and PCV13 [for all groups], and Bexsero[®] [for Group 2]) may be given as per standard of care at the last study visit after completion of study procedures (Visit 5 at 13 to 14 months). For Group 2, Bexsero[®] will be provided by the Sponsor to complete the vaccination series for subjects enrolled in this group. Subjects in Group 3 will be offered a single dose of the licensed ACWY conjugate meningococcal vaccine (Nimenrix[®]). This is a non-study vaccine to be administered 30 days after the last study visit (Visit 5) at an additional optional visit, and will be outside the scope of the study evaluations. No immunogenicity and safety data will be collected after the administration of these vaccines.

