6.1.1.3 Dose Selection and Timing

- Subjects in Group 1 will receive 2 doses of MenACYW conjugate vaccine administered concomitantly with routine pediatric vaccines (1st dose at 3 months of age) or with Bexsero[®] (2nd dose at 12 to 13 months of age).
- Subjects in Group 2 will receive 2 doses of MenACYW conjugate vaccine administered concomitantly with routine pediatric vaccines (1st dose at 3 months of age) or alone (2nd dose at 12 to 13 months of age).

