6.1.2.3 Dose Selection and Timing

- Subjects in Group 1 will receive 3 doses of Bexsero[®] administered at 2, 4 and 12 to 13 months of age.
- Subjects in Group 2 will receive 2 doses of Bexsero[®] administered at 2 and 4 months of age. (Note: The 3rd dose of Bexsero[®] will be given at 13 to 14 months of age [Visit 5] after completion of study procedures, and will be provided by the Sponsor in order to complete the vaccination series).
- Subjects in Group 3 will receive 3 doses of Bexsero[®] administered at 2, 4 and 12 to 13 months of age.

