12.2.2.1 Overall Safety Analysis Set for Any Dose (SafAS)

The overall SafAS is defined as those subjects who have received at least one dose of the study vaccine and have any safety data available.

All subjects will have their safety analyzed after any dose according to the vaccine received from Visit 1 (2 months) to Visit 4 (12 through 13 months).

- 1) If one subject received both MenACYW conjugate vaccine and Bexsero[®] vaccine at Visit 4, the actual vaccination group is “Group 1”.
- 2) Else if one subject only completed Visit 1 and received Bexsero[®] at Visit 1, the actual vaccination group will be classified as “Group 1”, “Group 2” or “Group 3” according to the randomization group.
- 3) Else if one subject did not receive both MenACYW conjugate vaccine and Bexsero[®] vaccine at Visit 4, but received at least one dose of MenACYW from Visit 1 to Visit 4, the actual vaccination group is either “Group 1” or “Group 2” based on the randomization group.
- 4) Else if one subject did not receive MenACYW conjugate vaccine but received at least one dose of Bexsero[®] vaccine from Visit 1 to Visit 4, the actual vaccination group is “Group 3”.
- 5) Else if one subject did not receive MenACYW conjugate vaccine and Bexsero[®] vaccine from Visit 1 to Visit 4, but received at least one dose of routine vaccines from Visit 1 to Visit 4, the actual vaccination group is “Other”

The safety analysis tables will not present data for ‘Other’ group, and the safety data for ‘Other’ group will be listed only.

Safety data recorded for a vaccine received out of the protocol design will be excluded from the analysis (and listed separately).

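### The PPAS3 definition, which carries the primary non-inferiority test, states the Visit 4 vaccines of Groups 1 and 2 the wrong way round and addresses its exclusion list to PPAS2

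*Protocol*

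**What the plan says.** Section 12.2.3.3 of the protocol builds PPAS3 in three steps: a list of exclusion bullets, a sentence about invalid Visit 5 results, and a sentence saying which Visit 4 vaccines count as correct for each group.

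- **Correctness sentence.** It requires "the dose of MenACYW conjugate vaccine for Group 1, the dose of MenACYW conjugate vaccine and the dose of Bexsero[®] for Group 2", and Bexsero for Group 3.
- **Randomized schedule.** Section 5.1.1 gives "Group 2: MenACYW conjugate vaccine at 3 months and at 12 to 13 months of age; Bexsero[®] at 2 and 4 months of age". Section 6.1.1.3 describes the two MenACYW doses in Group 2 as "administered concomitantly with routine pediatric vaccines (1st dose at 3 months of age) or alone (2nd dose at 12 to 13 months of age". Section 6.1.2.3 states "Subjects in Group 2 will receive 2 doses of Bexsero[®] administered at 2 and 4 months of age" and places the third Bexsero dose at Visit 5, after study procedures. Group 1 receives both vaccines at Visit 4. Table 5.1 and the Visit 4 steps in Section 5.1.4 agree.
- **Safety set.** Rule 1 in Section 12.2.2.1 reads "If one subject received both MenACYW conjugate vaccine and Bexsero[®] vaccine at Visit 4, the actual vaccination group is" Group 1.
- **PPAS3 exclusion list.** It opens with "The subjects presenting with at least one of the following relevant protocol deviations will be excluded from the PPAS2", although it stands under the PPAS3 heading. One bullet is "Subject did not complete the vaccination schedule, including the infant schedule and the 12 to 13 months vaccination in second year of life"; another excludes children given a vaccine other than the randomized one between Visits 1 and 4. The sentence after the list begins "In addition to the reasons listed above, subjects will also be excluded from the PPAS3".

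**The concern.** The primary endpoint (Section 9.1.2.1) is hSBA seroprotection 30 days after the Visit 4 vaccination, Group 1 against Group 2. Section 12.2 puts the immunogenicity analyses on the per-protocol sets and makes the full analysis sets exploratory. PPAS1 rests on Visit 3 serology and PPAS2 on Visit 4 serology before the toddler dose, so PPAS3 is the only per-protocol set that can hold the primary data. That it is the single confirmatory set is an inference from these sections, but no other set fits.

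Its definition contains two incompatible membership rules. A Group 2 child vaccinated exactly as randomized passes the bullets and fails the correctness sentence. The bullets that reveal the intended meaning are, by the letter of their lead sentence, addressed to a different set. The trial is open-label, and the PPAS3 definition already leaves some deviations to the clinical team's judgement before database lock. The written rule should not add a further point to be settled by interpretation.

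**Working it through.** **1. The plan's own figures.** Planned evaluable children (Section 12.5): 320 × 0.70 = 224 in each of Groups 1 and 2, and 160 × 0.70 = 112 in Group 3. Overall power from Table 12.1: 0.959 × 0.925 × 0.998 × 0.998 = 0.8835, which matches the tabled 88.4%. As a cross-check, exact binomial enumeration of the planned Wilson-score lower limit with 224 per group and equal true rates gives 0.9663 (A), 0.9325 (C) and 0.9985 (Y and W each). The product is 0.898, within two percentage points of the stated value. These figures describe the set as intended.

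**2. Visit 4 vaccines, side by side.**

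| Group | Schedule (5.1.1, Table 5.1, 5.1.4, 6.1.1.3, 6.1.2.3) | PPAS3 correctness sentence (12.2.3.3) |
|---|---|---|
| 1 | MenACYW + Bexsero | MenACYW |
| 2 | MenACYW | MenACYW + Bexsero |
| 3 | Bexsero | Bexsero |

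The parallel sentences for PPAS1 and PPAS2 agree with the schedule. Only the one for PPAS3 does not.

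**3. Who qualifies if every rule in Section 12.2.3.3 is enforced as written.**

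| Child | Correctness sentence | Schedule and randomized-vaccine bullets |
|---|---|---|
| Group 1, both vaccines (as randomized) | met, if the sentence sets a minimum | met |
| Group 1, Bexsero missed | met | not met |
| Group 2, MenACYW alone (as randomized) | not met | met |
| Group 2, both vaccines (error) | met | not met |

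No Group 2 child passes both columns. By design none receives Bexsero at Visit 4, so 0 of the planned 224 remain and the primary difference could not be computed.

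**4. The PPAS2 label.** PPAS2 already has its own exclusion list in Section 12.2.3.2, which stops at a Visit 4 sample taken before the toddler dose. Applied literally, the second list would add Visit 4 vaccination and Visit 5 sampling conditions to the persistence set. That set draws on Subset B, about 90 children per group. If the 30% non-adherence is assumed to apply there too, 90 × 0.70 = 63 would be evaluable; the protocol gives no such figure.

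**5. After correction.** With the group labels and set name corrected, PPAS3 returns to 224 evaluable children in each of Groups 1 and 2, and the tabled 88.4% is unaffected.

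**The case against.** The strongest reply is that these are drafting slips with an obvious intended reading. Both bullets refer to the randomized schedule, which the rest of the protocol states consistently. They exclude a Group 1 child who missed Bexsero and a Group 2 child who wrongly received it, whatever the later sentence says. The PPAS3 heading, the opening line of the section and the sentence after the list all show which set is meant. Emptying the control arm would be noticed at once. The slip also offers no evident selective choice, because its literal effect falls on every correctly vaccinated Group 2 child alike, and Section 6.4 blinds the laboratory staff. Finally, the Group 1 clause is incomplete and not false, since Group 1 does receive MenACYW at Visit 4.

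Much of this stands. The intended rule can be recovered, 0 of 224 is a literal-reading result and not a forecast, and only the Group 2 clause flatly contradicts the schedule. The safety-set rule supports the group definition but is not a competing per-protocol rule. None of this makes the text right. The sentence is a working part of the set definition, and its counterparts for PPAS1 and PPAS2 are correct. Section 12.1 says the SAP is written in accordance with the protocol, so the error could carry into the derivation of the set.

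**Conclusion.** The concern holds. As written, the correctness sentence for PPAS3 contradicts the randomized schedule and the bullets in its own section, and the exclusion list names the wrong set. Enforced literally, the section leaves no Group 2 child in the primary analysis set. Under the intended rule there is no effect on sample size, power, margin or error rate, and no bias is claimed. This is therefore an error in a key definition, not a design flaw. The conclusion rests on reading the text directly and on the inference that PPAS3 is the confirmatory set. It does not depend on the power figures or on the assumed 63 children in the persistence set. The passages show no sign of redaction or damaged extraction, and they are current text, not an amendment log.

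**What to change.** Before database lock:

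1. Reconcile the correctness sentence in Section 12.2.3.3 with the Visit 4 vaccines each group is randomized to receive under Sections 5.1.1, 6.1.1.3 and 6.1.2.3. Cross-referring to Table 5.1 would avoid restating the schedule.
2. In the lead sentence of the exclusion list in Section 12.2.3.3, change the set named from PPAS2 to PPAS3.
3. Check that the SAP, which was not available for this review, and the derivation of PPAS2 and PPAS3 repeat neither error.

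The cost is two wording corrections and one check. Study conduct, sample size and power are unaffected.
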